#### **6.2.2.2. Procedure in Case of Pregnancy**

If a female subject or partner of a male subject becomes pregnant during the study dosing period or within 3 months from the discontinuation of dosing, the investigator should report the information to the study supporter as if it is an SAE. The expected date of delivery or expected date of the end of the pregnancy, last menstruation, estimated fertility date, pregnancy result and neonatal data etc., should be included in this information. The investigator will follow the medical status of the mother, as well as the fetus, as if the pregnancy is an SAE.

When the outcome of the pregnancy falls under the criteria for SAEs [spontaneous abortion, induced abortion, stillbirth, death of newborn, congenital anomaly (including anomaly in a miscarried fetus)], the investigator should respond in accordance with the report procedure for SAEs. Additional information regarding the outcome of a pregnancy (which is categorized as an SAE) is mentioned below.

- "Spontaneous abortion" includes abortion and missed abortion.
- Death of an infant within 1 month after birth should be reported as an SAE regardless of its relationship with the study drug.
- If an infant dies more than 1 month after the birth, it should be reported if a relationship between the death and intrauterine exposure to the study drug is judged as "possible" by the investigator.
- In the case of a delivery of a living newborn, the "normality" of the infant is evaluated at the birth.
- "Normality" of the miscarried fetus is evaluated by visual examination unless test results which indicate a congenital anomaly are obtained prior to miscarriage.

#### **6.2.2.3. SAE Reporting to Study Supporter ( Novartis Oncology)**

Any serious adverse events which occur during the clinical study or within 30 days of receiving the last dose of study medication, whether or not related to the study drug, must be reported by the investigator. In addition, any SAEs which occur as a result of protocol specific diagnostic procedures or interventions must also be reported.

All serious adverse events must be reported by facsimile within 24 hours to Novartis Oncology . MDC – Oncology [contact] (make sure you include the 1 prior to the 610 as this is a desktop fax)

The SAE report should comprise a full written summary, detailing relevant aspects of the adverse events in question. Where applicable, information from relevant hospital case records and autopsy reports should be included. Follow-up information should be forwarded to Novartis Oncology within 24 hours.

SAEs brought to the attention of the investigator at any time after cessation of eltromboapg and considered by the investigator to be related or possibly related to eltrombopag must be reported to Novartis Oncology if and when they occur. Additionally, in order to fulfill international reporting obligations, SAEs that are related to study participation (e.g., procedures, invasive tests, change from existing therapy) or are related to a concurrent medication will be collected and recorded from the time the subject consents to participate in the study until he/she is discharged.

#### **6.2.3. Secondary Efficacy Endpoints**

The key secondary endpoints for this study are:

- To evaluate the safety and tolerability of the combination of eltrombopag and decitabine. Safety will be assessed by the overall incidence and severity of all study-treatment related adverse events per CTCAE v 4.0
- To evaluate the incidence of dose reductions and delays of decitabine therapy
- To evaluate the effect of eltrombopag on medically significant hemorrhagic events (defined as Grade 3 or 4 hemorrhagic events on CTCAE v 4.0)
- To evaluate the effect of eltrombopag on platelet and RBC transfusion independence per IWG-2006 criteria
  - o Platelet IWG-2006: A complete response is defined as a platelet count  $> 100 \times 10^9/L$ ; and a major response defined as an increase of platelet count by higher than  $30 \times 10^9/L$ .
  - o Durable platelet count: in which a hematologic improvement in platelets (HI-P) defined as either an increase  $\geq 30 \times 10^9/L$  from patients with a baseline platelet count  $\geq 20 \times 10^9/L$ , or an increase from  $< 20 \times 10^9/L$  to  $\geq 20 \times 10^9/L$  and by at least 100%, present for  $\geq 8$  weeks.
- Incidence of transformation to AML per FAB criteria ( $>30\%$  blasts) during treatment period and follow-up
- Incidence and severity of bone marrow fibrosis during treatment period and follow-up
- To examine the relationship between clinical response with ferritin level and other markers of iron burden at study start

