### **3. STUDY ELIGIBILITY**

#### **3.1 Inclusion Criteria**

1. Signed, informed consent must be obtained prior to any study specific procedures.
2. Subjects with a histologically confirmed diagnosis of MDS by FAB criteria, including both MDS and RAEB-T (AML with 20-30% blasts and multilineage dysplasia) and chronic myelomonocytic leukemia (CMML) with at least 10% bone marrow blasts by World Health Organization (WHO) classification are eligible.
3. Advanced MDS by virtue of intermediate-2 or high-risk MDS by IPSS score, or high or very-high risk by IPSS-R.
4. Platelet count  $\leq 100 \times 10^9/L$  at baseline
5. Eastern Cooperative Oncology Group (ECOG) performance status of 0 to 2
6. Adequate liver function, as evidenced by a serum bilirubin  $\leq 2x$  the ULN (except for patients with a confirmed diagnosis of Gilbert's Disease) and an ALT or AST  $\leq 3x$  the laboratory ULN.
7. Serum creatinine  $\leq 2.5x$  upper limit of normal
8. Subjects must be  $\geq 18$  years of age at the time of informed consent
9. Subject is practicing an acceptable method of contraception (documented in chart). Female subjects (or female partners of male subject) must either be of non-childbearing potential (hysterectomy, bilateral oophorectomy, bilateral tubal ligation or post-menopausal  $> 1$  year), or of childbearing potential and use one of the following highly effective methods of contraception (i.e. Pearl index  $< 1.0\%$ ) from 2 weeks prior to administration of study medication, throughout the study, and 28 days after completion or premature discontinuation from the study:

- Complete abstinence from intercourse;
- Intrauterine device (IUD);
- Two forms of barrier contraception (diaphragm plus spermicide, and for males condom plus spermicide);
- Male partner is sterile prior to entry into the study and is the only partner of the female;
- Systemic contraceptives (combined or progesterone only).

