## 5.2 On-Study Procedures

PROCEDURES	Pre-Study Screen o	Cycle 1 Day 1	Cycle 1 Day 8 (+/- 2 days)	Cycle 1 Day 15 (+/- 2 days)	Cycle 1 Day 22 (+/- 2 days)	Day 1 Cycle 2 onwards (+/- 5 days)	End of Treatment Visit (+/- 5 days)	Safety Visit 28 days after last dose (+/- 28 days)
Informed Consent	X							
Eligibility	X	X						
Medical History	X							
Patient Weight	X							
Vital Signs	X	X	X	X	X	X	X	X
Physical Exam and Performance Status	X	X				X	X	X
Concomitant Medications	X	X	X	X	X	X	X	X
Transfusion and Supportive Care Assessment	X	X	X	X	X	X	X	X
CBC with differential	X*	X	X	X	X	X 	X	X 
Blood Chemistries (AST, ALT, bilirubin)	X** a	X	X	X	X	X 	X	X
12-lead EKG	X a							
Bone marrow aspiration and/or biopsy	X					X 	X	
IPSS score & WHO disease classification	X					X 	X	
Pregnancy Test	X†							
Investigational Drug Dispense		X				X		
AE and SAE assessment	X	X	X	X	X	X	X	X
Optional: Correlative studies 	X							

oScreening must be performed within 4 weeks prior to study drug initiation / study start unless otherwise indicated

\*CBC with differential and blood chemistries including iron studies (sodium, potassium, BUN, creatinine, glucose, calcium, phosphate, magnesium, AST, ALT, total bilirubin, alkaline phosphate, uric acid, serum iron, transferrin, transferrin saturation, total iron binding capacity and ferritin) must be performed within 72 hours of Cycle 1 Day 1

^Serum iron, transferrin, transferrin saturation, total iron binding capacity and ferritin are required only on Cycle 1 Day 1 and do not need to be repeated

aEKG, including QTc intervals, at screening or baseline. A follow-up EKG will be performed if a subject experiences a clinically relevant abnormality.

†Within 7 days of Day 1 in females of child-bearing potential

Weekly CBC with differential and blood chemistries required until stable counts, and weekly x4 weeks after any change in eltrombopag dosing

Weekly CBC with differential should be performed weekly for the 4 weeks after discontinuation of eltrombopag

Bone marrow aspiration and/or biopsy with cytogenetics required for study entry, and every cycle for the first 4 cycles for primary outcome, and then every 3 cycles as clinically indicated. Cytogenetics do not need to be repeated if normal at study start.

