### 6.2. Study Endpoints

**6.2.1. Primary Efficacy Endpoint:** The overall response rate (CR + PR + HI) based on the IWG-2006 criteria detailed below. Responses must last at least 4 weeks per definition.

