**Failure:**

- Death during treatment or disease progression characterized by worsening of cytopenias or significant increase in percentage of bone marrow blasts

**Hematologic Improvement (HI) Response Criteria\*:** responses must last at least 8 weeks

- **Erythroid response** (if pretreatment hemoglobin  $< 11g/dL$ )
  - Hemoglobin increase by  $\geq 1.5g/dL$
  - Relevant reduction of units of RBC transfusions by an absolute number of at least 4 RBC transfusions/8 wk compared with the pretreatment transfusion number in the previous 8 wks. Only RBC transfusions given for a Hgb of  $\leq 9.0 g/dL$  pretreatment will count in the RBC transfusion response evaluation
- **Platelet response** (if pretreatment platelets  $< 100 \times 10^9/L$ )
  - Absolute increase of  $\geq 30 \times 10^9/L$  for patients starting with  $> 20 \times 10^9/L$  platelets
  - Increase from  $< 20 \times 10^9/L$  to  $> 20 \times 10^9/L$  and by at least 100%
- **Neutrophil response** (if pretreatment  $< 1.0 \times 10^9/L$ )
  - At least 100% increase and an absolute increase of  $> 0.5 \times 10^9/L$

\*Pretreatment counts averages of at least 2 measurements (not influenced by transfusions) for at least one week

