## 8.3. Analysis of Key Study Endpoints

The primary endpoint is overall response rate (ORR). The ORR will be evaluated along with the exact 95% confidence interval. Secondary endpoints include platelet response, durable platelet response, transformation to AML, incidence of bone marrow fibrosis, and time-to-event outcomes such as progression-free survival (PFS) and overall survival (OS). The probabilities of PFS and OS will be estimated using the method of Kaplan and Meier. The incidence rates of other binary secondary endpoints will be estimated, along with the exact 95% confidence intervals. Subjects that discontinue the study prior to having achieved a clinical response will be considered to have not had an event.

**Patients receiving growth factors other than eltrombopag (erythropoietin, GM-CSF or G-CSF) will not be considered in the HI analysis for the time periods specified in Section 4.5.3 Supportive Care Guidelines. Hemoglobin levels and platelet counts collected from patients that have received a transfusion within the last 7 days will not be considered in the analysis.**

Survival or times to failure and time to progression functions will be estimated using the Kaplan-Meier method. The two-sided log-rank test will be used to assess the differences of time to events between groups.

The total number of dose administrations, the average dose (mg), and the cumulative dose administered will be summarized by eltrombopag treatment group.

Blood chemistry and complete blood counts will be summarized by treatment group at each time point.

Additional exploratory analyses of the key study endpoints will be performed as deemed appropriate.

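### The secondary platelet complete response, labelled IWG-2006, asks only for a count above 100 × 10⁹/L, so a patient who enters just under 100 can qualify on ordinary fluctuation

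*Combined protocol and SAP*

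**What the plan says.** Section 6.2.3 places the platelet definitions under the transfusion-independence endpoint. The first reads "Platelet IWG-2006: A complete response is defined as a platelet count" above 100 × 10⁹/L, "and a major response defined as an increase of platelet count by higher than" 30 × 10⁹/L. Neither part gives a duration or a second count, and the complete response has no condition on baseline. The next item is a separate endpoint, "Durable platelet count: in which a hematologic improvement in platelets (HI-P) defined as either an increase" of at least 30 (or a doubling from below 20 to at least 20), present for at least 8 weeks.

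Four other places bear on this:

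- **Section 3.1** sets the entry limit: "Platelet count $\leq 100 \times 10^9/L$ at baseline". A patient at 95, 99 or exactly 100 is eligible.
- **Section 6.2.1 (primary endpoint)** says "Responses must last at least 4 weeks per definition". Its hematologic improvement criteria add "responses must last at least 8 weeks", and its platelet criterion needs a rise of at least 30, or a doubling from below 20, measured from an average of at least two pretreatment counts.
- **Section 5.2, footnote 1**: "Weekly CBC with differential and blood chemistries required until stable counts", and weekly again for 4 weeks after any change of eltrombopag dose.
- **Section 8.3**: "Secondary endpoints include platelet response, durable platelet response, transformation to AML". Binary secondary endpoints get exact 95% confidence intervals. Platelet counts within 7 days of a transfusion are not used.

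**The concern.** A response category should separate patients who changed from patients who did not. Because the entry ceiling and the complete-response threshold are the same number, the highest category is the easiest to reach for the least thrombocytopenic patients. It can be reached with no change in the underlying level. The chance also grows with the number of counts taken, which differs between patients because each dose change triggers four more weekly counts.

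The definition also carries the IWG-2006 label while differing from the IWG-2006 platelet criterion that the same protocol sets out in 6.2.1. A reader of the results would not know which rule produced the rate.

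With no control arm, chance crossings cannot be subtracted. An exact confidence interval describes sampling error in the observed proportion, not misclassification of the patients in it.

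**Working it through.** The plan gives no rate, power or sample size for this endpoint, so there is no figure to reproduce.

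**Step 1: the definitions side by side (counts in 10⁹/L)**

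| | Threshold | Rise over baseline | Duration or confirmation |
|---|---|---|---|
| Complete response, 6.2.3 | > 100 | none | none |
| Major response, 6.2.3 | none | > 30 | none |
| Durable HI-P, 6.2.3 | ≥ 20 if baseline < 20 | ≥ 30, or doubling from < 20 | ≥ 8 weeks |
| HI platelet response, 6.2.1 | > 20 if baseline < 20 | ≥ 30, or doubling from < 20 | ≥ 8 weeks |

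With entry allowed at 100 or below, 99 to 101 (a rise of 2) or 100 to 101 (a rise of 1) meets the first row and no other. This step needs no assumption.

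**Step 2: number of counts**

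Cycle 1 Days 8, 15 and 22 and Day 1 of Cycles 2, 3 and 4 give 6 scheduled counts after baseline. Weekly counts through four 28-day cycles would give about 16.

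**Step 3: chance of qualifying with no change in the true level**

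Assume normal, independent counts with mean μ and within-patient coefficient of variation CV. Then P(at least one of k counts > 100) = 1 − Φ((100 − μ)/(CV·μ))^k. The documents give no CV, so a range is shown.

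- μ = 90, CV 15%: SD = 13.5, z = 10/13.5 = 0.741, Φ = 0.7706. For k = 4: 1 − 0.7706⁴ = 0.65. For k = 8: 1 − 0.7706⁸ = 0.88.
- μ = 85, CV 10%: SD = 8.5, z = 1.765, Φ = 0.9612. k = 4: 0.15. k = 8: 0.27.
- μ = 95, CV 10%: SD = 9.5, z = 0.526, Φ = 0.7007. k = 4: 0.76. k = 8: 0.94.

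A simulation that admits only patients with an observed baseline of 100 or below, for CV 5% to 20% and 6 later counts, gives 61–95% at a true level of 95, 8–87% at 90 and 0–9% at 70. The problem therefore sits near the entry ceiling.

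**Step 4: relaxing the assumptions**

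| Case | μ = 90, CV 15%: k = 4 / 8 | μ = 95, CV 10%: k = 4 / 8 |
|---|---|---|
| Independent, unchanged mean | 65% / 88% | 76% / 94% |
| AR(1) correlation 0.8 (assumed) | 42% / 57% | 51% / 67% |
| Mean falls by 20% (assumed), independent | 2% / 4% | 0.3% / 0.6% |

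If entry also requires a two-count baseline average of 100 or below, the 8-count figures at correlation 0.8 are 50% and 58%.

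**Step 5: what a rise and a confirming count do**

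Require a count above 100 and a rise of at least 30 over the two-count baseline average, both met at two consecutive counts out of 8. For correlations of 0, 0.5 and 0.8, chance qualifiers fall to about 2–6% (μ = 90, CV 15%) and 0.2–1% (μ = 95, CV 10%). The plan's durable HI-P rule, taken as 8 consecutive weekly counts, admits at most about 2.6% for true levels of 70 to 99 even at CV 20%.

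**The case against.** **Duration might be imported.** Section 6.2.1 has a 4-week rule for responses and an 8-week rule for hematologic improvement, and 6.2.3 uses the same IWG-2006 label. But those rules are written under the primary endpoint, and 6.2.3 does not refer to them. The existence of a separate durable category in 6.2.3 and 8.3 points the other way. Import is arguable, not stated.

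**The link to 8.3 is an inference.** Section 8.3 does not define platelet response, and the only criterion under that name is the stricter one in 6.2.1. Section 8.1 lists transfusion independence and does not name platelet response at all. This stands. The separate listing of durable response favours the 6.2.3 definition, but a reader who takes it as certain that the exact interval will be put on the bare count goes beyond the text.

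**The percentages are near a worst case.** This also stands. Section 4.1 says that thrombocytopenia most often appears or worsens in the first cycles, and a 20% fall in the mean nearly removes the effect. Eltrombopag may offset such a fall and counts recover between cycles, so that case is a bound and not an estimate.

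**Importance is limited.** The endpoint is descriptive, with no test or decision rule attached. Section 2.2 names transfusions and hemorrhage as the basis of clinically meaningful outcomes. The 8-week HI-P is reported alongside, and the 7-day rule already removes transfusion artefact, though not ordinary fluctuation. All of this argues for minor weight. It does not remove the gap in the definition.

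**Conclusion.** The point holds as a minor defect in a secondary definition. Section 6.2.3 as written can classify an unchanged patient as a complete responder, and it departs from the plan's own IWG-2006 platelet criterion. That conclusion rests on the text alone.

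Its size does not. The 65% and 88% figures apply to a single hypothetical patient with an unchanged mean of 90, an assumed CV of 15% and independent counts. They are an upper-end illustration. The documents give neither the within-patient variability nor the share of patients entering near 100, so no effect on the trial's reported rate can be calculated.

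Two stronger readings are tempting and are not supported. A reader might infer that the ORR or the futility rule is inflated, but the ORR's platelet component uses the 6.2.1 criterion with a rise and 8 weeks. A reader might also infer that the plan has no protection against transient platelet rises, but the durable endpoint and the transfusion exclusion provide some.

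**What to change.** 1. In 6.2.3, count a complete response only if the count is above 100 and the patient also meets the rise in the 6.2.1 platelet criterion, measured from the averaged pretreatment count. A patient going from below 20 to above 100 meets that rise automatically.
2. Require complete and major response to be confirmed at the next scheduled count at least 1 week later. State the interval: with the ±2-day windows, the Cycle 1 Day 8 and Day 15 visits can fall on Days 10 and 13, only 3 days apart.
3. Apply the 7-day transfusion exclusion of 8.3 to both counts.
4. State in 8.3 that platelet response means this definition, and whether it pools complete and major response.
5. Keep the 8-week HI-P as the separate durable response.

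The cost is wording only, since the counts are already scheduled and the increment is the plan's own. The downside is a somewhat lower platelet response rate. A patient entering at 95 would need 125, and complete response becomes nearly a subset of major response. If that is thought too strict, tabulating the rate by baseline count would at least show where the responders come from.

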### **1.2 Secondary Objectives**

The secondary objectives of the study are:

- To evaluate the safety and tolerability of the combination of eltrombopag and decitabine. Safety will be assessed by the overall incidence and severity of all study-treatment related adverse events per CTCAE v 4.0
- To evaluate the incidence of dose reductions and delays of decitabine therapy
- To evaluate the effect of eltrombopag on medically significant hemorrhagic events (defined as Grade 3 or 4 hemorrhagic events on CTCAE v 4.0)
- To evaluate the effect of eltrombopag on platelet and RBC transfusion independence per IWG-2006 criteria
- Incidence of transformation to AML per FAB criteria (>30% blasts) during treatment period and follow-up
- Incidence and severity of bone marrow fibrosis during treatment period and follow-up
- To examine the relationship between clinical response with ferritin level and other markers of iron burden at study start

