### **4.2. Study Duration**

4.2.1. All subjects must complete a screening visit, day 1 visits for each new cycle, an end of treatment visit and whenever possible, an end of study safety visit 28 days after the last dose of eltrombopag.

4.2.2. Treatment will continue until discontinuation due to relapse, unacceptable toxicity, or disease progression as defined by the IWG 2006 criteria for MDS. This includes:

- clinically significant progressive disease at any time, or

- a lack of clinical benefit after 4 cycles of treatment at the highest dose of study medication, or
- Possibility of undergoing allogeneic stem cell transplantation
- discontinuation of study drug for more than 6 weeks, or
- intercurrent illness that prevents further administration of treatment, or
- unacceptable adverse event(s), or
- patient decision for study withdrawal, or
- general or specific changes in the patient's condition that render the patient unacceptable for further treatment in the judgement of the investigator

4.2.3. Study cycles will be administered every 28 days  $\pm$  5 days or upon resolution of any clinically significant study drug related AE to grade 0-1, whichever occurs first. If a subsequent cycle is delayed due to adverse events related to decitabine, or if it is considered in the best interest of the patient to delay administration of decitabine (e.g. because of concern for an infection), administration of the eltrombopag may continue as planned.

4.2.4. Administration of subsequent cycles should be administered when neutrophils recover to  $\geq 1 \times 10^9/L$  and platelets to  $\geq 30 \times 10^9/L$  or to baseline levels prior to the start of the last cycle of therapy. Patients with residual disease may start the next cycle with neutrophil and/or platelet counts lower than these if judged to be in the best interest of the patient to start the next cycle. The decision to treat should be documented in the patient's medical record.

4.2.5. Patients may remain on study for up to 12 cycles if the patient demonstrates clinical benefit and no excessive toxicity (i.e. no clinically significant study-drug related grade  $\geq 3$  toxicity). Patients who are experiencing clinical benefit and have not experienced excessive toxicity may be eligible to continue therapy after discussion with the PI and the discussion documented in the patient's medical record.

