### 5.3. End of Study Visit:

Subjects will undergo an End of Treatment Visit at the time of discontinuation of eltrombopag. A bone marrow biopsy and/or aspirate with cytogenetics for IPSS and WHO classification will be performed at this visit. Cytogenetics can be omitted if diploid at study start.

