## 8. Statistical Considerations

This is an open label, phase II clinical trial to evaluate the efficacy of eltrombopag in combination with decitabine as a frontline therapy in patients with Intermediate-2 or High-Risk Myelodysplastic Syndrome (MDS). A total of 40 patients will be accrued from M.D. Anderson Cancer Center (MDACC), at a rate of 2-3 patients per month.

The primary endpoint is the overall response rate (ORR) based on the IWG-2006 criteria, which includes complete remission (CR), partial remission (PR), and hematologic improvement (HI). Patients' overall response will be assessed during the first four 28-day cycles of treatment. Patients who drop off the study early due to treatment-related toxicities will be counted as treatment failures (i.e., non-responders).

The method of Thall, Simon and Estey [1995] will be used for futility and toxicity monitoring for this study. The target overall response rate is 60% and the following futility stopping rule will be applied in cohort size of 10, starting from the 10th patient:  $\text{prob}\{p(\text{ORR}) < 0.6\} > 0.95$ , where  $p(\text{ORR})$  denotes the overall response rate. That is, the trial will be stopped early due to futility, if during the study we determine that there is more than 95% chance that the ORR is less than 60%. Assuming that the prior distribution of  $p(\text{ORR})$  is beta (1.2, 0.8), the stopping boundaries corresponding to this futility monitoring rule are shown below in Table 1. The operating characteristics (OCs) for this futility stopping rule are summarized in Table 2. The design software Multic Lean Desktop (version 1.2.0) developed by the Department of Biostatistics at M. D. Anderson Cancer Center (MDACC) was used to generate the futility stopping boundaries and the

OC table. In order to utilize the software for the design, a highly informative beta (600, 400) prior was assumed to approximate the target 60% overall response rate.

Table 1. Futility stopping boundaries in cohort size of 10.

Number of patients	Stop the trial if there are this many patients achieving overall response
10	0-3
20	0-8
30	0-13

Table 2. Operating characteristics for futility monitoring in cohort size of 10 (max sample size = 40).

True ORR	Prob(stop the trial early due to futility)	Average sample size
0.3	0.971	14.8
0.4	0.775	22.0
0.5	0.391	31.3
0.6	0.105	37.5
0.7	0.015	39.6

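### AML transformation is any marrow above 30% blasts while entry allows 20-30%, so counting error alone can label some unchanged patients as transformed

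*Combined protocol and SAP*

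**What the plan says.** Inclusion criterion 2 (Section 3.1) admits MDS by FAB criteria, "including both MDS and RAEB-T (AML with 20-30% blasts and multilineage dysplasia". The AML endpoint appears in Section 1.2 as "Incidence of transformation to AML per FAB criteria (>30% blasts) during treatment period and follow-up" and is repeated in Section 6.2.3 ("Incidence of transformation to AML per FAB criteria", with the same threshold) with no further condition. The upper end of the entry band is therefore the event line.

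Marrows are taken "every cycle for the first 4 cycles for primary outcome, and then every 3 cycles as clinically indicated" (Section 5.2, footnote 3). Section 5.3 adds one at the end of treatment: "A bone marrow biopsy and/or aspirate with cytogenetics for IPSS and WHO classification will be performed at this visit". Section 4.2 states "Patients may remain on study for up to 12 cycles".

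Section 8.1 reports binary secondary endpoints as incidence with an exact 95% interval, and time to AML by Kaplan-Meier. The disease progression list in Section 6.2.1 requires, for patients with 20-30% blasts, an increase of at least 50% to above 30%. That condition is not carried over to AML transformation. Responses must persist (4 weeks, or 8 weeks for hematologic improvement); transformation has no persistence rule.

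**The concern.** A threshold endpoint placed at the edge of the eligibility range, tested repeatedly and met by a single crossing, picks up measurement error as well as disease change. Every scheduled marrow gives a patient with stable blasts just under 30% another chance to cross. Such crossings would count in the AML incidence and as events in the time-to-AML curve. Their number depends on how many patients happen to enter at 20-30%, so one pooled rate mixes true transformation with the case mix at entry.

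The two blast rules also disagree: the same small rise can be AML transformation without meeting the blast criterion for progression.

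**Working it through.** The plan gives no expected rate, event count or precision for AML transformation, so there is no figure to reproduce.

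**Inputs from the documents.** Entry band 20-30% (Section 3.1); event above 30% (Sections 1.2 and 6.2.3); progression rule of at least a 50% rise to above 30% (Section 6.2.1); marrows in each of the first 4 cycles, then every 3 cycles, plus end of treatment (Sections 5.2 and 5.3); 40 patients (Section 8).

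**Assumptions, not in the documents.** Cells counted (200 or 500); independent binomial counting error only; the spread of true blasts; their course on treatment; the share of patients in the band.

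**1. The two rules side by side.** For entry at 25%, blast progression needs 1.5 × 25% = 37.5%. A marrow of 31% is AML transformation but not blast progression.

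**2. Number of looks.** Four in cycles 1-4. A patient treated for 12 cycles would have about 4 + 2 + 1 = 7, if the later marrows are done. Four are used below unless stated.

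**3. One patient with constant true blasts p.** Per marrow, q = P(X > 0.30N) with X ~ Binomial(N, p). Over k marrows, the chance of at least one crossing is 1 − (1 − q)^k.

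| Cells N | True blasts p | q | k = 4 | k = 7 |
|---|---|---|---|---|
| 200 | 22% | 0.003 | 0.013 | 0.022 |
| 200 | 25% | 0.045 | 0.17 | 0.28 |
| 200 | 28% | 0.24 | 0.66 | 0.85 |
| 500 | 25% | 0.005 | 0.02 | 0.03 |
| 500 | 28% | 0.15 | 0.47 | 0.67 |

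The risk sits in the upper half of the band.

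**4. Average over the band.** Simulation with true blasts between 15% and 30%, either spread evenly or declining exponentially from 15% (scale 5 percentage points), kept if the entry count reads 20-30%, then four later marrows. Entries are the proportion with any marrow above 30%.

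| Spread | Cells | Unchanged | Half have a 25% fall | All have a 25% fall |
|---|---|---|---|---|
| Even | 200 | 25% | 13% | 0.2% |
| Even | 500 | 16% | 8% | <0.1% |
| Near 20% | 200 | 11% | 5% | 0.1% |
| Near 20% | 500 | 6% | 3.2% | <0.1% |

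Letting true blasts run to 35% gives 35% and 23% (even) and 13% and 8% (near 20%). Those figures include entrants whose true blasts already exceed 30%: with even spread and 200 cells they supply 37% of the crossings. Their later readings are correct by the plan's own threshold, so they are excluded above.

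**5. Effect on the trial.** If 20% of patients (8 of 40) enter in the band:
- Upper end: 0.20 × 25% = 5 points; 40 × 0.05 = 2 patients.
- Lower end, half with a blast fall: 0.20 × 3.2% = 0.6 points; 40 × 0.0064 = about 0.3 patients.

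Both scale in proportion to the share assumed. If all such patients have a 25% fall, the effect is near zero.

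**6. What stricter rules would leave** (unchanged disease, four marrows, same spreads).
- Rise of at least 50% over entry, alone: about 1% (even, 200 cells); below 0.1% (500 cells).
- That rise, or a second marrow above 30% at any later look: about 9% and 6% (even, 200 and 500 cells); about 3% and 2% (near 20%).

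**The case against.** The strongest reply has four parts.

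First, above 30% is the FAB cut-point, so adding conditions refines a named criterion and does not correct an error. That stands, and it is why the FAB count should remain.

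Second, unchanged blasts in everyone is the extreme case in a trial of active treatment with a 60% response target. That stands in part. Response here includes hematologic improvement, so it does not equate to blast reduction, but the lower figures in the table are as plausible as the upper ones. A reader might infer that the bias exceeds 5 points in the band under any assumption, or that it reaches about 35%. Neither holds: the first fails once blasts fall, and the second needs entrants whose true blasts are already above 30%.

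Third, little depends on this endpoint. It is descriptive, and neither the response rate nor a stopping rule uses it. An exact 95% interval at 4 of 40 runs from 2.8% to 23.7%, wider than the bias. A reader might infer that a comparison with other series is spoiled or that a false harm signal follows. The plan proposes no such comparison and lists AML under efficacy endpoints, apart from the adverse-event summary. Still, a wide interval does not remove a one-directional bias.

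Fourth, mandatory confirmation could lose true events: after cycle 4 marrows are every 3 cycles and only as indicated, and patients may leave or die first. That stands, and rules out confirmation as the sole definition.

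**Conclusion.** The point holds in a limited form. The event line is the top of the entry band, one crossing suffices, and the plan's own progression rule for that band is stricter. Patients near 30% with stable disease can be counted as transformed.

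The size rests on assumptions the documents cannot settle: about 6% to 25% of patients entering at 20-30% if disease is unchanged, about half that if half have a 25% blast fall, and near zero if all do. At an assumed 20% share this is roughly 0.6 to 5 points of overall incidence. Sampling-site and reader variation are left out and would raise the rates. Patients with true blasts of 15% or less are essentially unaffected. This is an improvement to consider; it does not threaten the primary result.

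**What to change.** In Sections 6.2.3 and 8.1, keep the FAB count above 30% as defined, and report AML incidence and time to AML separately for entry blasts below 20% and 20-30%.

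For the 20-30% group add a parallel count, dated at the first marrow above 30%. It accepts an event only if at least one of these applies:
- it also shows the rise of at least 50% over entry already used in Section 6.2.1;
- it is confirmed on a later scheduled or end-of-treatment marrow;
- it is a clinical diagnosis of AML.

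Report how many events qualify by each route. The rise criterion alone carries about 1% false events with 200 cells (even spread), whereas accepting either the rise or a second marrow leaves about 2-9%.

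The cost is a sentence or two in each section and no new procedures. The stricter count can miss or delay some true transformations, which is why the FAB count stays beside it.
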